8. TRIAL DESIGN

This is a prospective, open-label, outcome adjudicated multicentre randomised controlled trial (RCT) evaluating the use of a CEP device in participants with aortic valve stenosis planned for treatment by TAVI. TAVI will be carried out in specialist cardiac centres. Trial participants will be randomised with equal allocation to TAVI with CEP treatment or TAVI without CEP treatment (the current UK standard of care). Randomisation will be coordinated by the LSHTM CTU (London School of Hygiene and Tropical Medicine Clinical Trials Unit) via a secure website and stratified by centre using random permuted blocks.

8.1. Justification for all-comer study design

There are no statistical models to identify accurately a higher risk population that could inform a stratified approach. The trial will therefore allow a comprehensive assessment of the experimental treatment strategy in an unselected population and may subsequently inform the development of a risk prediction model.

8.2. Study population

At each participating centre all patients with aortic stenosis who are scheduled for TAVI will be considered for the trial. The technical suitability for the use of CEP will be left to the discretion of the treating physician. Relative contra-indications to the use of CEP include severe proximal stenosis or congenital variation of the anatomy of the left common carotid and right brachiocephalic arteries (e.g. complex non-standard anatomy such as bovine arch or aberrant right subclavian), or no vascular access options via the right upper limb. In order that this population reflects a general population of patients with aortic stenosis who are considered suitable for TAVI we have identified no other specific exclusion criteria.

9. PARTICIPANT IDENTIFICATION

9.1. Trial Participants

The target population for this trial is patients with severe aortic stenosis undergoing treatment by TAVI.

9.2. Inclusion Criteria

- Participant is willing and able to give informed consent for participation in the trial
- Aged 18 years or above
- Considered to be candidates for TAVI by the clinical team (via any access route where CEP may be used)
- Participant is suitable for treatment with the cerebral embolic protection device in the opinion of the treating physician.

9.3. Exclusion Criteria

We have identified no specific exclusion criteria. Participants involved in observational studies will be eligible for this study. As this is an all-comer design, current or previous participation in other ongoing randomised trials will not be disqualifying for recruitment to this study unless treatment is expected to impact on the effect of using a CEP device on stroke.

10. TRIAL PROCEDURES

10.1. Screening and Eligibility Assessment

The clinical team at the recruiting centres (Participating centres and participant identification centres) will consider all patients who are considered to be candidates for TAVI by the supervising clinician.

Screening will take place prior to consent and randomisation. It will be done by the treating clinical team (or delegated member of the direct care team) using patient notes. There will be no access by the research team to patient identifiable data prior to consent.

10.2. Informed Consent

Only patients who give consent will be included in the trial. If informed consent is not possible, the patient will not be recruited into the trial. Consent will be taken prior to the patient's scheduled TAVI procedure. The patient will be allowed as much time as wished to consider the participant information sheet and the opportunity to question the Investigator, or other independent parties to decide whether to participate in the trial.

If possible, Informed Consent will be obtained in writing by means of a patient dated signature and a dated witness signature of the person who presented the Informed Consent Form.

Oral consent (over the telephone or by videoconference) is also permissible. This will be documented using the approved remote consent form. Baseline data can be collected once consent has been recorded in this manner. However, the participant must personally sign and date the remote consent form to confirm their participation in the trial when they attend hospital. They must sign and date the form before randomisation can take place.

The person who obtained the consent must be suitably qualified and experienced, have been authorised to do so by the Chief/Principal Investigator and authorisation documented on a trial delegation log. One copy of the signed Informed Consent Form will be given to the participant, one copy will be kept in the local trial site file and the original will be placed in the patient's medical records.

For the purposes of informed consent monitoring, redacted consent forms may be requested by the LSHTM CTU and will be sent by secure email.

10.3. Randomisation

Randomisation of consenting patients will be performed following consent by the staff delegated by the local PI to be responsible for randomisation at each hospital using a web-based randomisation system (Sealed Envelope). Best practice is for randomisation to be carried out as near as possible to the time of the patient's scheduled TAVI procedure. However, randomisation must be performed before the start of the TAVI procedure which is defined as first arterial puncture.

Randomisation will be done as follows:

The delegated member of staff will access the randomisation system at sealedenvelope.com

- They will confirm the eligibility criteria for the patient (see section 9.2 and 9.3):
- To complete randomisation of the patient, the delegated member of staff will need to enter their
 password and click "Confirm. This will generate the treatment allocation to either TAVI (standard
 of care) or TAVI with CEP (intervention). The allocation will be received as an on-screen notification
 and via email to the investigator. This information will be directly available to the doctor
 performing the TAVI and, if allocated, the CEP implementation.
- Randomisation will create the CRF record for the patient and will automatically be logged.

10.4. Access to the online randomisation service

Access to the randomisation site sealedenvelope.com will only be available to staff delegated by the local PI (Principal Investigator) to be responsible for randomisation. Delegation and training logs will be recorded at both the local research team and at the LSHTM CTU. Randomisation training includes a demonstration of the system and training in the trial eligibility criteria. These will be provided at the site initiation visit in the first instance, and then locally by previously trained staff for newly delegated researchers. Each staff member will have a unique account for accessing the randomisation site, and must not share these details of their account with other staff members.

If a staff member is unable to access their account, they can follow the password reset instructions on sealedenvelope.com or contact the LSHTM CTU to request an account reset at [contact]. Please note that the LSHTM CTU is available for account resets between the hours of 8am – 5pm, Monday to Friday.

10.5. Blinding and code-breaking

Unblinded staff:

This is an open-label trial. Hospital staff will be aware of the allocation of patients.

Blinded trial staff:

As an open-label trial there will be no blinded staff. However, the clinical events committee will be blinded to trial treatment. Supporting documentation sent to the committee will be redacted by staff at the LSHTM CTU.

10.6. Trial procedures table

·	Visit T-2: Initial patient approach (e.g.: clinical visit*)	Visit T-1: Informed consent obtained, baseline assessments (Clinical or study visit)	TAVI procedure (Clinical visit)	During hospital admission for TAVI**		Visit 1: In person (clinical visit) or by phone (study visit)	Visit 2: In person (clinical visit) or by phone (study visit)	
			Day 0	Day 1	Day 2	72-hours post- TAVI or discharge if sooner	6-8 weeks post- TAVI	12-months post- TAVI
Eligibility assessment (clinical care team)	X							
Informed consent		X						
Baseline assessments		X						
Randomisation			X					
TAVI with CEP (intervention arm) OR TAVI without CEP (standard of care)			x					
Stroke status assessed by clinical team review				х	х	х		
Questionnaire to Verify Stroke Free Status (QVSFS)				х	х	х		
National Institute of Health Stroke Score (NIHSS)***						х		
Simple modified Rankin scale questionnaire (smRSq) ***		х				х	х	х
Stroke physician assessment***				Х	Х	Х		
Mortality status						Х	Х	Х
Vascular access site injury						Х	Х	
EQ-5D-5L		Х					Х	Х
Adverse event reporting			Х	Х	Х	X	Х	
API Study questionnaire****						X		

^{*} Clinic visit refers to non-study visits. These are routine hospital attendances as part of standard care.

^{**} During the patient's in-hospital stay the QVSFS will be administered daily up to and including 72 hours or discharge from hospital, whichever is earlier.

^{***} Only be administered if the participant's QVSFS indicated the possible presence of a stroke.

^{****}Only for BHF PROTECT-TAVI participants who consent to take part in the API Study

10.7. Baseline assessments

Visit T-2 Initial patient approach at pre-procedure visit (done by clinical care team)

- Eligibility assessment (prior to visit)
- Patient information sheet provided if patient eligible
- Patient invited to join study

Visit T-1 Informed consent and baseline data collection (during clinical visit or study visit either in person or over the telephone/videoconference)

Baseline data can be collected at any time from consent up to the time of the patient's TAVI procedure.

- Informed consent collected
- Demographics
- Medical history
- Upload standard of care imaging (CT and echo)
- Concomitant medications
- smRSa
 - Short questionnaire administered for the study
- EQ-5D-5L
 - Short questionnaire administered for the study

TAVI Procedure

- Randomisation (this will be done by the cardiologist or other delegated staff member)
- The start of the TAVI procedure is defined as first arterial puncture.
- TAVI with CEP (intervention arm)
 - The TAVI procedure takes approximately 90 minutes and is done by a cardiologist. The
 CEP adds approximately 5 minutes to the procedure and is done by the cardiologist.
- TAVI without CEP (standard of care) (control arm)
 - The TAVI procedure takes approximately 90 minutes and is done by a cardiologist.

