15.1. Source Data

Source documents are where data are first recorded, and from which participants' CRF data are obtained. These include, but are not limited to, hospital records (from which medical history and previous and concurrent medication may be summarised into the CRF), clinical and office charts, laboratory and pharmacy records, diaries, microfiches, radiographs, and correspondence.

CRF entries will be considered source data if the CRF is the site of the original recording (e.g. EQ-5D-5L where there is no other written or electronic record of data). All documents will be stored safely in confidential conditions. On all trial-specific documents, other than the signed consent, the participant will be referred to by the trial participant number/code, not by name.

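### Section 10.7 lets baseline EQ-5D-5L and smRSq be taken after randomisation, when open-label staff already know the allocation, contrary to the order in table 10.6

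*Protocol*

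**What the plan says.** - **Baseline window (10.7).** "Baseline data can be collected at any time from consent up to the time of the patient's TAVI procedure". The items listed are demographics, medical history, imaging upload, medications, smRSq and EQ-5D-5L. The same section adds: "The start of the TAVI procedure is defined as first arterial puncture".
- **Randomisation window (10.3).** Randomisation follows consent, and "randomisation must be performed before the start of the TAVI procedure which is defined as first arterial puncture". There is also advice on timing: "Best practice is for randomisation to be carried out as near as possible to the time of the patient's scheduled TAVI procedure".
- **Who knows the allocation, and when.** Under 10.3 the result appears on screen and is sent "via email to the investigator. This information will be directly available to the doctor" performing the TAVI. Section 10.5 says: "Hospital staff will be aware of the allocation of patients".
- **Procedures table (10.6).** Baseline assessments, EQ-5D-5L and smRSq are marked at Visit T-1. Randomisation is marked at Day 0.
- **Recording.** Section 10.3: "Randomisation will create the CRF record for the patient and will automatically be logged". Section 15.1: "CRF entries will be considered source data if the CRF is the site of the original recording", with EQ-5D-5L as its example. Section 20.7 mentions a paper CRF kept at site.

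**The concern.** A baseline value is protected by randomisation only if it is fixed before the allocation is known. Once staff know the arm, a questionnaire score or a recorded risk factor can drift with it, and the value becomes a post-randomisation measurement. EQ-5D-5L and smRSq are the exposed items because both rest on judgement and are administered for the study.

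Two uses are at stake. Section 14.6 estimates QALY change from EQ-5D-5L at baseline and 12 months. Section 14.1 builds a stroke-risk model and asks whether the effect of CEP depends on underlying risk; it does not limit the risk factors to data recorded before allocation. The timing of collection is a conduct rule, so an analysis plan cannot put it right afterwards.

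**Working it through.** The plan states no figure on this point, so the check is mainly of sequence.

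1. **Permitted orders.** Write C for consent, B for baseline, R for randomisation and P for first arterial puncture. Section 10.7 requires C, then B, with B no later than P. Section 10.3 requires C, then R, then P. Two orders satisfy both rules: C–B–R–P and C–R–B–P. Table 10.6 shows only the first. The sentence in 10.7 is wider than the table.

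2. **Is there a gate?** Where the protocol wants a condition on randomisation, it writes one. Section 10.2 requires the remote consent form to be signed first, and 10.3 requires eligibility to be confirmed. Neither asks for completed baseline data.

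3. **Is the allocation known in the second order?** Yes for staff, at once (10.3, 10.5). The protocol does not say whether patients are told before the procedure.

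4. **Which analyses use the baseline?**
   - Primary stroke comparison (14.1): an intention-to-treat risk ratio and risk difference, with no baseline adjustment described. Not affected.
   - QALY analysis (14.6): baseline EQ-5D-5L enters directly.
   - Stroke-risk model (14.1): exposed in so far as risk factors are recorded late. History already in hospital records (15.1) is less open to influence.
   - Disability outcome (7.2, item 10): smRSq at discharge, 6–8 weeks and 12 months in participants with stroke. No change from baseline is specified.

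5. **Can the size be computed?** Before any covariate adjustment, the direct shift in the QALY difference is w × f × d. Here w is the weight of baseline in the area under the utility curve, f the share of baselines taken late (taken as equal in both arms), and d the mean between-arm shift among them.
   - w follows from the schedule. With two points (baseline and 12 months, as 14.6 names), w = 0.5. If the 6–8 week EQ-5D-5L in table 10.6 is also used, w = (6/52)/2 = 0.058 to (8/52)/2 = 0.077.
   - f and d are not given, so no bias can be computed.

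6. **Illustration, on assumed values only.** Suppose f × d, the shift averaged over all participants, is 0.005 to 0.01.
   - Two points: 0.5 × 0.005 = 0.0025 to 0.5 × 0.01 = 0.005 QALY.
   - Three points: 0.058 × 0.005 = 0.0003 to 0.077 × 0.01 = 0.0008 QALY.
   - For comparison, the planned 3% v 2% (14.2) with an assumed utility loss of 0.2 to 0.4 per stroke over one year gives 0.01 × 0.2 = 0.002 to 0.01 × 0.4 = 0.004 QALY.
   - If only 10% of baselines were late, d would have to be 0.005/0.10 = 0.05 to 0.01/0.10 = 0.10 to produce that average shift.

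On these assumptions the result runs from well below the expected gain to about its size, depending on inputs that the protocol does not fix.

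**The case against.** The strongest reply is that the protocol's structure already puts baseline first. Table 10.6 does so. Section 10.7 lists the baseline items under Visit T-1 and opens a separate block for the TAVI procedure with randomisation as its first item, so the window could be read as closing at that block. Section 10.2 lets baseline data be collected once remote consent is recorded, before the in-hospital signature that must precede randomisation. The advice to randomise close to the procedure keeps the exposed interval short.

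Most of this stands as a limit on likelihood. It does not remove the gap. Section 10.7 itself defines the start of the procedure as arterial puncture, and the timing of randomisation is best practice rather than a rule, so it may come earlier than the procedure block.

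A reader might go further in four ways that the documents do not support:
- *That sites will commonly collect baseline late because the CRF record is created at randomisation.* Creation of the record governs data entry, not when a questionnaire is given, and a paper CRF exists.
- *That the bias could cancel the whole expected QALY gain.* That needs an unsourced shift and the two-point weight of 0.5.
- *That the disability outcome is biased through its baseline smRSq.* No analysis using it as a reference is described.
- *That the primary result is at risk.* No baseline covariate enters it.

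It is also fair to say that the fix comes late. Recruitment began in October 2020 (7.2) and is planned for 58 months. Version 6.0 is dated July 2024, about 45 months in, which left about 58 − 45 = 13 months.

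**Conclusion.** The point holds as a fault in a stated rule. Sections 10.7 and 10.3 together permit baseline EQ-5D-5L and smRSq to be taken after open-label staff know the arm, and this conflicts with the order in 10.6. The conclusion rests on the wording of those sections and on the definition of procedure start as first arterial puncture.

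Its reach is limited to secondary analyses: chiefly the QALY estimate, and to a lesser degree the risk-stratified analysis. How often it occurs, and how large any bias is, cannot be derived from the protocol; the figures in the illustration are assumptions and not an estimate. The change is still worth making, because it costs almost nothing and restores the sequence that the table already shows.

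**What to change.** - **10.7:** state that baseline data, including EQ-5D-5L and smRSq, are completed and dated after consent and before randomisation.
- **10.3:** add baseline completion to the confirmation made before randomisation, recorded on paper or on a form that is available before the CRF record is created.
- **10.6:** align the table with this rule.
- **Participants already enrolled:** where questionnaire completion dates and times are available, report by arm how many baselines followed randomisation. Times of entry into the electronic CRF will not serve, because the record exists only from randomisation onwards. The protocol does not say that completion times are recorded, so this may be possible only in part.
- **Sensitivity analysis:** repeat the QALY analysis without relying on the late baseline values, for example by setting them to missing and imputing them from data recorded before randomisation. Keep the participants in the analysis; dropping them would be a post-randomisation exclusion.

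Cost: one sentence, one confirmation item and one alignment of the table. No assessment is added and the sample size does not change. The small downside is that sites cannot randomise until two short questionnaires are done.

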10.8. Subsequent visits

Please refer to section 10.6 for the table of trial procedures.

10.8.1. In hospital

This will be carried out daily up to and including 72 hours post-TAVI, or until discharge if sooner.

Primary outcome

- Stroke status
 - Assessed by routine clinical assessment post-TAVI, supported by the framework provided by the QVSFS.
 - If after routine clinical assessment, the participant is reviewed by the local stroke team, a Stroke Form must be completed.
 - o If the participant answers YES to any of the questions on the QVSFS, this will prompt a local outcome assessment against the stroke definition described in section 7.1.2. and the diagnosis will be recorded on the Stroke Form in the eCRF, with supporting information as required. If a stroke is diagnosed by the stroke team, severity is assessed using NIHSS and recovery is assessed using smRSq
 - Short questionnaires administered for the study

Secondary outcomes

- Mortality status
 - Taken from patient notes
- Vascular injury
 - Taken from patient notes

- Safety reporting
 - Taken from patient notes

The API Study

The API Study Questionnaire is only completed by participants who have consented to take part in the API study (see Section 12). The questionnaire is self-administered and should be completed following the patient's TAVI procedure up to 72 hours post-TAVI or hospital discharge (if sooner).

10.8.2. Visit 1 – 6-8 weeks post-TAVI

This will be conducted by telephone for the study, however if there is a pre-scheduled clinical visit, it can be done in person.

Contact with the patient will be arranged by a delegated member of the research team at the local hospital. Phone calls are projected to take no more than 10 minutes to complete the EQ-5D-5L questionnaire. The staff contacting the patient will check electronic records prior to contacting the patient to ensure they have not died. While participant preferences for contact will take priority, we advise that after 3 unsuccessful attempts to reach the patient no further attempts are made.

Secondary outcomes assessed:

- Mortality status
 - Taken from patient notes
- smRSq
 - Short questionnaire administered for the study (only done in presence of a stroke outcome)
- EQ-5D-5L
 - Short questionnaire administered for the study
- Vascular injury
 - Taken from patient notes
- Safety reporting
 - Taken from patient notes

10.8.3. Visit 2 – 12 months post-TAVI

This will be conducted by telephone for the study, however if there is a pre-scheduled clinical visit, it can be done in person.

Contact with the patient will be arranged by a delegated member of the research team at the local hospital. Phone calls are projected to take no more than 10 minutes to complete the EQ-5D-5L questionnaire. The staff contacting the patient will check electronic records prior to contacting the patient to ensure they have not died. While participant preferences for contact will take priority, we advise that after 3 unsuccessful attempts to reach the patient, no further attempts are made.

Secondary outcomes assessed:

- Mortality status
 - Taken from patient notes
- smRSq
 - Short questionnaire administered for the study
- EQ-5D-5L
 - Short questionnaire administered for the study

10.9. Sample Handling

No additional samples will be taken as part of this research study.

10.10. Participant withdrawal

According to the design of the trial, participants have the following three options for withdrawal;

- 1) Participants may withdraw from active follow-up and further communication but allow the trial team to continue to access their medical records and any relevant hospital data that is recorded as part of routine standard of care; i.e., CT-Scans, blood results and disease progression data etc.
- Participants can withdraw from the study but permit data obtained up until the point of withdrawal to be retained for use in the study analysis. No further data would be collected after withdrawal.
- 3) Participants can withdraw completely from the study and withdraw the data collected up until the point of withdrawal. The data already collected would not be used in the final study analysis. (Any limits to this type of withdrawal where, for example analysis of their data has already been integrated into interim results will be explained in the participant information sheet).

The type of withdrawal and reason for withdrawal, if known, will be recorded in the CRF (Case Report Form). Withdrawal from the trial will not influence future healthcare in anyway.

